10.2 Randomization

10.2.1 Allocation- sequence generation

Eligible patients will be allocated in an equal ratio, using a computer randomization procedure. The allocation sequence will be prepared by an independent statistician appointed by the international steering group. The randomization procedure will accommodate availability of each treatment such that a patient cannot be allocated to an unavailable treatment. There will be no stratification of the allocation sequence, only simple randomization.

10.2.2 Allocation- procedure to randomize a patient

Eligible patients will be entered into the www.who.int/COVIDcore database including patient baseline details and available treatment arms at the study site. Patients will then be randomized to one of the available arms. The allocation will be registered in the patient's journal and in the eCRF system (Viedoc). This is an open-label study and no steps to conceal allocation are necessary. The study statistician will be blinded to the randomization allocation for the writing of the national statistical analysis plan (SAP). The authorisations bound to role of the study statistician in the eCRF when reading or downloading data will ensure that the statistician won't see the treatment allocation until database lock.

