The Investigational NOR-SOLIDARITY protocol

[figure not shown]
Project title

The NOR Solidarity multicenter trial on the efficacy of different anti-viral drugs in SARS-CoV-2 infected patients

Short title: The NOR-SOLIDARITY trial

EudraCT no: 2020-000982-18

Version: 12 2020-06-11

CONFIDENTIAL

This document is confidential and the property of the study group. No part of it may be transmitted, reproduced, published, or used without prior written authorisation.

STATEMENT OF COMPLIANCE

This document is a protocol for a clinical research study. The study will be conducted in compliance with all stipulations of this protocol, the conditions of Regional Ethic committee approval and the latest version of the Helsinki Declaration.

This protocol describes a multicenter add-on trial that is part of and based on the global WHO COVID-19 core protocol. The aim of the WHO COVID-19 core protocol is to evaluate and compare four different antiviral treatment regimens on in-hospital mortality in moderate and severe COVID infected patients. This multicenter add-on trial will be a separate and independent trial but will use the global level randomization and contribute to report endpoints and adverse events to the global trial.

Synopsis of the protocol

Terminology: The novel coronavirus-induced disease first described in 2019 in China is designated COVID-19 (or COVID), and the pathogen itself (an RNA virus) is SARS-coronavirus-2 (SARS-CoV-2). The Norwegian study that is an adapted WHO-study and follows the WHO protocol whilst also analyzing additional factors is referred to as the NOR-SOLIDARITY study. Standard of Care will be referred to as SoC.

Background: In early 2020 there were no approved anti-viral treatments for COVID, and WHO expert groups advised that four re-purposed drugs, Hydroxychloroquine, Remdesivir, Lopinavir with Ritonavir and Interferon (β 1a) should be evaluated in an international five-arm randomized trial where the fifth arm is SoC. The NOR-SOLIDARITY study started analyzing the effects of Hydroxychloroquine and Remdesivir initially and may open for a fourth arm.

Notification: Hydroxychloroquine was removed as treatment option by the steering committee on June 8th 2020 due to lack of evidence confirmed both in internal WHO interim analyses and an external report from the Recovery study. Thus, from this date, June 8th 2020, NOR-Solidarity allocate patients only to SoC and SoC+ Remdesivir.

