Patient enrolment and randomization: This will be carried out online via a database created for this purpose by the WHO. Adults (age \geq 18 years) recently hospitalized, or already in hospital, with definite COVID and, in the view of the responsible doctor, no contra-indication to any of the study drugs will be randomly allocated between

- Local SoC alone,
OR local SoC plus
- Remdesivir

Data reported before randomization via the WHO database:

- Hospital and randomizing doctor
- Confirmation that informed consent has been obtained
- Patient identifiers, age and sex
- Patient characteristics (yes/no): current smoking, diabetes, heart disease, chronic lung disease, chronic liver disease, asthma, HIV infection, active tuberculosis.
- COVID-19 severity at entry (yes/no): shortness of breath, being given oxygen, already on a ventilator, and, if lungs imaged, major bilateral abnormality (infiltrations/patchy shadowing)
- Whether the study drug is currently NOT AVAILABLE at the hospital.

Inclusion criteria

1. Adult patients, 18 years and older
2. Confirmed SARS-CoV-2 infection by PCR
3. Admitted to the hospital ward or the ICU
4. Subjects (or legally authorized representative) provide informed consent prior to initiation of the study
5. No anticipated transfer within 72 hours to a non-study hospital

Exclusion criteria

1. Severe co-morbidity with life expectancy $<$ 3 months according to investigators assessment
2. ASAT/ALAT $>$ 5 times the upper limit of normal
3. Acute co-morbidity within 7 days before inclusion such as myocardial infarction
4. Known intolerance to the study drug
5. Pregnancy or breast feeding
6. Any reason why, in the opinion of the investigators, the patient should not participate

7. Participation in a potentially confounding drug or device trial during the course of the study
8. Already receiving any of the current study drug(s)
9. Patients on concomitant medications, which is part of the list of prohibited medications have to be excluded from the current study.

Prohibited medication:

Haloperidol, carbamazepine, phenytoin, rifampin, phenobarbital, isoniazid, pyrazinamide, nevirapine, ritonavir, sodium valproate/valproic acid

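### Section 10.2.2 waives allocation concealment because the trial is open-label; with two arms left, an entry that Remdesivir is unavailable makes standard of care certain, and no rule shown keeps such patients out of the comparison

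*Protocol*

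**What the plan says.** Section 10.2.1 sets out simple randomisation without stratification, from a sequence prepared by an independent statistician: "Eligible patients will be allocated in an equal ratio, using a computer randomization procedure". It adds a restriction: "The randomization procedure will accommodate availability of each treatment such that a patient cannot be allocated to an unavailable treatment".

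Section 10.2.2 describes the order of events. First, "Eligible patients will be entered into the www.who.int/COVIDcore database including patient baseline details and available treatment arms at the study site". Next, "Patients will then be randomized to one of the available arms". It then states "This is an open-label study and no steps to conceal allocation are necessary", and goes on to the blinding of the study statistician.

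The Synopsis has a list headed "Data reported before randomization via the WHO database". Besides the hospital, the randomising doctor, consent and baseline characteristics, it contains this item: "Whether the study drug is currently NOT AVAILABLE at the hospital".

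The Synopsis notification, repeated in Section 2.1, says that from 8 June 2020 "NOR-Solidarity allocate patients only to SoC and SoC+ Remdesivir".

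Section 10.3 makes intention-to-treat the primary population and puts every randomised participant in it. It makes no exception for patients who had only one arm open to them.

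**The concern.** Two separate safeguards are run together. Blinding keeps the treatment unknown after assignment, and an open-label trial gives it up. Concealment keeps the assignment unknown until the patient is irrevocably in the trial. An open-label trial needs concealment more than a blinded one does, because little else protects the comparability of the arms. Being open-label is therefore no reason to waive it.

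The sentence would be only a slip of wording if the procedure closed every route to knowing an assignment in advance. It leaves one open. Availability is entered with the patient's details before allocation, and it limits the arms on offer. With several active arms, a missing drug only narrowed the choice. With one active arm left, a missing drug leaves SoC alone, so the result is known before the patient is entered and nothing is randomised.

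Such patients would still count as SoC controls. If they differ in prognosis from the others, or cluster in periods when care or case mix was different, the SoC arm is no longer a fair comparator for intensive care or for mortality. This can happen without misconduct, for example through genuine stock-outs at particular sites or times.

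**Working it through.** **Step 1: the logic of the procedure.** The inputs are Sections 10.2.1 and 10.2.2, the Synopsis list of pre-randomisation data and the notification of 8 June 2020.

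- Remdesivir reported available: P(SoC) = 0.5 and P(Remdesivir) = 0.5. Randomisation is simple, without blocks or strata, so earlier allocations say nothing about the next one.
- Remdesivir reported unavailable: P(SoC) = 1 and P(Remdesivir) = 0.
- No entry gives P(Remdesivir) = 1.

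If a share u of entries is marked unavailable, the SoC share of all entered patients is u + (1 − u)/2 = (1 + u)/2. That is 52.5%, 55% and 60% for u = 5%, 10% and 20%, so the equal ratio is lost as well.

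**Step 2: the plan's own figure.** Section 10.1 gives 26% intensive care, a 10-point difference, a 2.5% two-sided level, 90% power and 406 per group. With the unpooled normal formula:

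n = (2.241 + 1.282)² × (0.26 × 0.74 + 0.16 × 0.84) / 0.10² = 12.41 × 0.3268 / 0.01 = 405.6, rounded up to 406.

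The figure reproduces. It is not in dispute and serves only to scale the illustration: N = 2 × 406 = 812, with a one-sided nominal false-benefit rate of 2.5%/2 = 1.25%.

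**Step 3: illustration.** From the protocol: N = 812, overall risk p = 0.26, critical value 2.241. Assumed, with no source in the protocol: Remdesivir has no effect, a share u of entries is marked unavailable, and those patients have k times the average risk.

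- Risk in the forced-SoC patients: kp.
- Risk in the rest: r = p(1 − uk)/(1 − u). This is the Remdesivir rate.
- SoC rate: [u·kp + (1 − u)r/2] / [(1 + u)/2].
- Spurious difference, SoC minus Remdesivir: 2up(k − 1)/(1 − u²).
- False-benefit rate: Φ(difference/SE − 2.241).

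For u = 0.10 and k = 1.5:

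- Forced patients: 1.5 × 0.26 = 0.39. The rest: (0.26 − 0.039)/0.90 = 0.2456.
- SoC rate: (0.039 + 0.1105)/0.55 = 0.2718.
- Difference: 0.2718 − 0.2456 = 0.0263.
- Group sizes: 0.55 × 812 = 446.6 and 365.4.
- SE = √(0.2718 × 0.7282/446.6 + 0.2456 × 0.7544/365.4) = 0.0308.
- Φ(0.852 − 2.241) = Φ(−1.389) = 8.2%.

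| u | k | Spurious difference | False-benefit rate (nominal 1.25%) |
|---|---|---|---|
| any | 1 | 0 | 1.25% |
| 5% | 1.25 | 0.65 points | 2.1% |
| 10% | 1.5 | 2.63 points | 8.2% |
| 15% | 1.5 | 3.99 points | 17.1% |

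Defining the excess risk relative to the other patients, rather than to the average, changes little: with u = 10% and a ratio of 1.5, the difference is 2.3 points and the two-sided error 6.6%, against 2.5%.

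The sign follows k − 1. With u = 10% and k = 0.5, the difference is 2 × 0.10 × 0.26 × (−0.5)/0.99 = −2.63 points, which counts against Remdesivir.

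**The case against.** The case on the other side is substantial.

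- **The sequence is concealed in practice.** Randomisation is central and online, the sequence comes from an independent statistician, and consent and baseline data are entered first. This stands for every patient entered with Remdesivir available. A reader might infer that the doctor can know or choose the next assignment in general; the documents do not support that. The route runs one way, to SoC, and only through the availability entry.
- **Availability is worded as a fact about the hospital or site.** Misusing it would need a false report. The randomising doctor is recorded, Section 5.3 refers to inventory logs, and monitors check adherence and source data (Section 1.3). A doctor who does not want the infusion also has open routes: exclusion criterion 6 in Section 4.2, or the freedom to discontinue described in Section 9.4. That the doctor makes the availability entry personally is an inference. All this weakens the motive for a false report, but it does nothing about genuine stock-outs that track site, time or case mix.
- **The direction is not established.** A reader might infer that sicker patients would be steered to SoC, flattering Remdesivir. Section 7.4.1 expects particular benefit in patients admitted to intensive care, and an investigator who shares that view would act the other way.
- **The size rests on assumed inputs.** That is correct. Moreover, Section 10.5.1 analyses patients with severe disease at entry separately, which limits imbalance in severity, though not in frailty or calendar time.
- **Unseen documents may settle it.** The primary analysis follows the WHO core protocol and its analysis plan. Those, the operating procedures and the national analysis plan are not at hand, and any of them may handle patients with one open arm. The protocol's own text does not, and its statement on concealment is wrong whatever they say.

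**Conclusion.** The point holds in limited form. The sentence in Section 10.2.2 is wrong in its reasoning and should not stand. Separately, with two arms left, an availability entry made before randomisation can make SoC certain, and the protocol shows no rule that keeps such patients out of randomisation or the primary population.

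Whether this biases the result depends on facts the protocol does not give: how often Remdesivir is reported unavailable, and whether that is related to prognosis or calendar time. If it is unrelated, there is no bias. If it is related, the bias can go either way. The figure of about 2.6 points and 8% false benefit against 1.25% shows what moderate departures could do under the stated assumptions. It is not an estimate for this trial, and nothing in the protocol suggests that availability has been misreported.

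The change is worth making because the gap is written into the procedure and is cheap to close.

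**What to change.** 1. In Section 10.2.2, replace the sentence with: *Allocation is concealed: the assignment is released by the central system only after consent, eligibility and baseline data are irrevocably entered.*
2. In Section 10.2.1, add: *Availability is a site-level stock status, documented before a patient is considered for the trial. While only SoC and Remdesivir are open, no patient is randomised when Remdesivir is unavailable at the site.*
3. If the WHO system cannot be changed, add to Section 10.3: *Patients entered with only one available arm are excluded from the randomised comparison.*

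The cost is a few sentences and a site instruction. Moving the availability field to site level may need a change by WHO, since randomisation is run globally; item 3 is the fallback. A few patients who present during stock-outs are lost to enrolment (and so to the total-population analyses) or, under item 3, to the comparison only. With one arm open they carry no randomised information on Remdesivir.

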10.2.3 Blinding and emergency unblinding

This is an open-label study. However, the staff at the central laboratory at OUS as well as the statistician responsible for analysis of the data will be blinded to the treatment allocation for the writing of the SAP.

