Assess the effect of Remdesivir on 28 days mortality, viral clearance, kidney and myocardial failure, co-infections, organ dysfunction and health-related Quality of Life.	Assessed during hospitalization 
 • Viral clearance as assessed by SARS-CoV-2 PCR in oropharyngeal specimens during hospitalization • Occurrence of kidney failure (eGFR <40 mL/min) • Occurrence of myocardial involvement assessed by biochemical markers as well as echocardiography measuring left ventricular ejection fraction within the first week • Occurrence of co-infections (super infections with bacteria, fungi and other virus) Assessed after 28 days 
 • Overall survival • Patient reported respiratory health status by CAT (Chronic Obstructive Pulmonary Disease (COPD) assessment Test) score Assessed after 3 months 
 • Occurrence of systolic and diastolic cardiac dysfunction and level of remodelling assessed by echocardiography and biochemical markers • Occurrence of pulmonary dysfunction and level of fibrosis assessed by spirometry and thoracic CT scan • Health related quality of life assessed by the RAND 36-item Short Form Health Survey (SF-36) item scores and the 5-dimension EuroQol (EQ-5D) questionnaires index value.
Exploratory (as addition to the WHO protocol)	

Assess the effect of Remdesivir on biomarkers and its safety.	Biomarkers during hospitalization and after 3 months 
 • Inflammatory and anti-inflammatory mediators as assessed in serum and plasma • Markers of extracellular matrix remodelling • Markers of endothelial activation • Markers of platelet activation • Cellular immunity • Prognostic biosignatures (RNA) • Gut microbiota assessed by rectal swab • Pharmacokinetics during hospitalization • Adverse events during hospitalization
---	--

4 Study population

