9.2 Procedures in Case of Emergency

The investigator is responsible for assuring that there are procedures and expertise available to cope with emergencies during the study. The study is not blinded and code breaking procedures is therefore unnecessary.

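### The blinding section does not cover the readers of echocardiograms and thoracic CT scans, on which three secondary endpoints partly rest, and ties even the laboratory's masking to the writing of the SAP

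*Protocol*

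**What the plan says.** The trial is open-label. Section 10.2.3 makes one exception: "the staff at the central laboratory at OUS as well as the statistician responsible for analysis of the data will be blinded". The sentence limits this in its closing words: these people "will be blinded to the treatment allocation for the writing of the SAP". For the statistician, section 10.2.2 goes further, since eCRF access rights "will ensure that the statistician won't see the treatment allocation until database lock". The laboratory staff have no matching statement.

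Section 10.2.2 also says that "The allocation will be registered in the patient's journal and in the eCRF system (Viedoc"), and that an open-label study needs no steps to conceal allocation. Section 9.2 confirms: "The study is not blinded and code breaking procedures is therefore unnecessary".

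The endpoint table in section 3 lists three secondary endpoints that use echocardiography or thoracic CT:

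- during hospitalization, myocardial involvement, from biochemical markers and echocardiographic left ventricular ejection fraction (LVEF) in the first week;
- at 3 months, "Occurrence of systolic and diastolic cardiac dysfunction and level of remodelling assessed by echocardiography and biochemical markers";
- at 3 months, "Occurrence of pulmonary dysfunction and level of fibrosis assessed by spirometry and thoracic CT scan".

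Section 7.1 schedules these examinations as study data. Section 10.5.2 compares secondary efficacy endpoints between arms in the ITT and per-protocol populations, with p-values and 95% confidence limits. The protocol does not say who reads the images or what the reader knows.

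**The concern.** The protocol accepts that masked assessment is useful but applies it where judgement matters least. Section 7.5 describes the research laboratory's methods as multiplex technology, immune assays on a robot platform and proteomics. A borderline LVEF, a diastolic classification, a judgement of remodelling and the extent of fibrosis on CT depend more on the reader.

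Giving a drug openly does not require reading images openly. A stored echocardiogram or CT scan can be assessed without the arm in view, and the 3-month examinations come long after a 10-day course. If readers know the arm and expect benefit, small shifts in borderline calls can create a difference between arms. The opposite expectation can hide one. The analysis cannot undo this, because masking has to be in place when the reading is made. It therefore belongs in the protocol and cannot be left to the SAP.

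**Working it through.** **Who is masked, and for what**

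| Group | Masked? | Scope | Place |
|---|---|---|---|
| Statistician | yes | writing of the SAP; no allocation seen until database lock | 10.2.2, 10.2.3 |
| Central laboratory staff | yes | writing of the SAP, as worded | 10.2.3 |
| Echocardiogram readers | not mentioned | – | – |
| Thoracic CT readers | not mentioned | – | – |

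Laboratory staff do not write the SAP. Read literally, section 10.2.3 therefore does not clearly mask any outcome measurement.

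**Counting the endpoints.** Section 3 lists three items that use echocardiography or CT. Both cardiac items also use biochemical markers, and the pulmonary item also uses spirometry. Imaging contributes to all three and is the sole basis of none.

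**The plan's own sample size.** The protocol has no figure on reader bias. Its 406 per group (section 10.1: 26% versus 16% receiving intensive care, two-sided 2.5%, 90% power) sets the upper end of the numbers used below and reproduces with unpooled variance:

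(2.2414 + 1.2816)² × (0.26×0.74 + 0.16×0.84) / 0.10² = 12.411 × 0.3268 / 0.01 = 405.6, rounded up to 406.

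**Illustration of the bias.** Assumptions, none of them from the protocol:

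- a true dysfunction rate of 30% in both arms, so no drug effect;
- a reader-induced shift that lowers the recorded rate in the remdesivir arm by 1, 3 or 5 points;
- a binary endpoint tested at two-sided 5%;
- n assessed per arm from 100 to 380.

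Formulas: SE = √{[p₁(1−p₁) + p₂(1−p₂)] / n}; z = (p₁ − p₂)/SE; chance of a false finding of benefit = 1 − Φ(1.96 − z). With no shift this is 2.5%.

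Worked cases:

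- 30% v 27%, n = 380: SE = √[(0.2100 + 0.1971)/380] = 0.0327; z = 0.917; 1 − Φ(1.043) = 0.148.
- 30% v 25%, n = 380: SE = √[(0.2100 + 0.1875)/380] = 0.0323; z = 1.546; 1 − Φ(0.414) = 0.339.
- 30% v 27%, n = 150: SE = √[(0.2100 + 0.1971)/150] = 0.0521; z = 0.576; 1 − Φ(1.384) = 0.083.

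The same formulas give:

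| Assessed per arm | 1-point shift | 3-point shift | 5-point shift |
|---|---|---|---|
| 100 | 3.6% | 6.8% | 12.2% |
| 150 | 3.8% | 8.3% | 16.1% |
| 200 | 4.1% | 9.8% | 20.1% |
| 380 | 4.9% | 14.8% | 33.9% |

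The bottom row is close to the best case for numbers. With 406 randomized and the protocol's assumed 5% control mortality, 406 × 0.95 = 385.7 survive to discharge, so 380 assessed means 380/385.7 = 98.5% attendance. Section 12 warns that enrolment may fall short, and section 10.4 allows analysis before 406 per arm if the global trial stops.

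**The case against.** The strongest reply is that the protocol is silent here, not contradictory. It declares an open-label design throughout, and reading procedures may be set in imaging or site instructions that are not shown. A reader might infer that the images will be read with the arm known. The protocol does not say so. What stands is that readers can see the allocation in the journal, and the section that lists who is masked leaves them out.

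A second reply is that the magnitude restates its own assumptions. This is right. The rate and the shifts are hypothetical, and the binary model does not fit LVEF, or graded fibrosis and remodelling, if these are analysed as continuous measures, for which section 10.5.2 plans mixed models or non-parametric methods. The table shows sensitivity and does not forecast the bias.

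Third, first-week echocardiography falls within the daily infusions, so whoever performs it at the bedside may see the treatment. This also stands and limits what masking can achieve.

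Four wider readings are tempting and are not supported:

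- **Four affected endpoints.** This count needs the pulmonary item split while the 3-month cardiac item stays whole. As listed, there are three.
- **Spirometry as a further case.** It depends on the effort of a patient who knows the allocation, and masking a reader does not change that.
- **Masked reading at almost no cost.** The protocol says nothing on cost or feasibility.
- **A threat to the main result.** In-hospital death needs no reader, and receipt of intensive care does not turn on who reads an echocardiogram or CT scan.

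**Conclusion.** The point holds for echocardiograms and thoracic CT scans. As written, section 10.2.3 leaves their readers unmasked for three secondary endpoints that are tested between arms, and words the laboratory's masking so narrowly that it does not clearly cover sample analysis.

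Under the stated assumptions, the chance of a false finding of benefit rises from 2.5% to between about 4% (1-point shift, 100 per arm) and about 34% (5-point shift, 380 per arm). The actual bias is unknown and could be nil. The primary analysis and the sample size are unaffected. This is a weakness in trial conduct that should be corrected, with consequences confined to these secondary endpoints.

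**What to change.** Amend section 10.2.3 as follows:

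1. The existing readers assess trial echocardiograms and thoracic CT scans for the three endpoints without being told the allocation. Requests carry the study number and not the arm, and the reading is recorded before the allocation in the journal is consulted.
2. Readings made with known allocation are flagged in the eCRF, and a sensitivity analysis takes account of them.
3. The masking of central laboratory staff covers the analysis of samples, and not only the period in which the SAP is written.

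Where masked reading is not feasible at a site, the protocol should say so and name it as a limitation.

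The change needs wording, a request-form instruction and a flag, with the same readers and no added examinations. Protection will be partial, because some urgent or bedside first-week echocardiograms will stay unmasked and readers keep access to the journal. No sample size or other figure in the protocol changes.
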